5.5.1 Blinding

Due to the nature and effects of sedative medication, study participation is not blinded for neither staff nor participants.

5.6 Study Variables

Variable number	Variable source	Variabel beskrivning	Variable name	Variable code	Variable characteristics	presentation	Analysis	Registration time /implantation
1.	CRF	QoR-15 pre	QoR-15 pre	0-10	ordinal	Manus 2	n, Median, interkvartil	CRF
2.	CRF	Trial subject nr	PtID	1-340	continuous			pre
3.	CRF	gender	gender	1=female 2=male	categorical/nominal	Table 1	% x/n	pre
4.	CRF	age	age	Number 18-105	continuous	Table 1	n, Median, min max, IQR	pre
5.	CRF	ASA	ASA	Number 1-5	ordinal	Table 1	P% x/n	pre
6.	CRF	weight	weight	30-250	continuous	Table 1	n, Median, min max, IQR	pre
7.	CRF	length	length	1,3-2,1	continuous	Table 1	n, Median, min max, IQR	pre
8.	CRF	Treatment strategy	strat	1= palliative 0=adjuvant	categorical/nominal	Table 1	P% x/n	pre
9.	CRF	patient arrival duva	Time duva	Hh:mm	continuous	Table 1	Derive preop tid Median, min max, IQR	pre
10.	CRF	patient arrival or	Time op	Hh:mm	continuous	Table 1	Derive preop tid Median, min max, IQR	pre
11.	CRF	heartrate	HR	30-150	continuous	Table 1	n, Median, min max, IQR	pre

12.	CRF	Saturation	SaO2	50-100	continuous	Table 1	n, Median, min max, IQR	pre
13.	CRF	BP systolisk	BT	60-230	continuous	Table 1	n, Median, min max, IQR	pre
14.	CRF	Laterality port	side	1= right 0=left	categorical/no minal	Table 2	P% x/n	pre
15.	CRF	Cath type	Cat type	0=BBraun 1=other	categorical/no minal	Table 2	P% x/n	pre
16.	CRF	Local anaestheti c volume	LA_vol	0-100 i ml	continuous	Table 2	n, Median, min max, IQR	intra
17.	CRF	Local anaestheti c type	LA type	0=carbocaine 1=lidnocaine 2=other	categorical/no minal	Table 2	P% x/n	intra
18.	CRF	LA adjuvans	LA	0=nej 1=natriumbikar bonat 2=adrenaline 3=nabi and adrenaline	categorical/no minal	Table 2	P% x/n	intra
19.	CRF	Vein	vein	0=v jugularis int 1=v subclavia 2=v femoralis	categorical/no minal	Table 2	P% x/n	intra
20.	CRF	Ultrasound guidande	US	1=yes 0=no	categorical/no minal	Table 2	P% x/n	intra
21.	CRF	Puncture number	punctnum ber	1-20	continuous	Table 2	n, Median, min max, IQR	intra
22.	CRF	Arterial puncture	apunct	0=no 1=yes	categorical/no minal	Table 2	P% x/n	intra
23.	CRF	Pneumoth orax	pnthx	0=no 1=yes	categorical/no minal	Table 2	P% x/n	intra
24.	CRF	Hematoma operating site	haemato m	0=no 1=yes	categorical/no minal	Table 2	P% x/n	intra
25.	CRF	Operator	operator	0 = ≤ 19 /year 1 = 20-49 /year	categorical/no minal	Table 2	P% x/n	intra

				2 = ≥ 50 / year				
26.	CRF	Help of colleague	colleague	0=no 1=yes	categorical/nominal	Table 2	P% x/n	intra
27.	CRF	Operating conditions	Op_cond	1-4	ordinal	Table 2	P% x/n	intra
28.	CRF	Aborted procedure	aborted	0=no 1=yes	categorical/nominal	Table 2	P% x/n	intra
29.	CRF	Position tip	Tip_pos	1=right atrium 2=distal v subclavia 3=other	categorical/nominal	Table 2	P% x/n	intra
30.	CRF	Op time	Op_time	minutes	continuous	Table 2	n, Median, min max, IQR	intra
31.	CRF	Sedation score at T1-4 (OAAS)	sedT1 sedT2 sedT3 sedT4	OAAS scale (0-5)	ordinal	Table 3	P% x/n	intra
32.	CRF	Sedation volym	DelVOL	Volume PCS ml	continuous	Table 3	n, Median, min max, IQR	intra
33.	CRF	Alfentanil delivered	DelALF	Alfentanil mg	continuous	Table 3	n, Median, min max, IQR	intra
34.	CRF	Propofol delivered	DelPROP	Propofol mg	continuous	Table 3	n, Median, min max, IQR	intra
35.	CRF	Rescue sedation	Resque_sed	0=no 1=yes	kategorisk/nominal	Table 3	P% x/n	intra
36.	CRF	Rescue reason	Rescue why	0=patient's request 1=operator's request 2=other	categorical/nominal	Table 3	P% x/n	intra

37.	CRF	Rescue type	Rescue type	0=propofol/ alfentanile 1=othert	categorical/no minal	Table 3		intra
38.	CRF	Hypoxia during procedure (SpO2<90 % or significant difference compared to baseline >5%SpO2)	hypoxia	0=no 1=yes	categorical/no minal	Table 3	P% x/n	intra
39.	CRF	Bradypnoea capnographic ≤8/min	RR	0=no 1=yes	categorical/no minal	Table 3	P% x/n	intra
40.	CRF	Chin lift	Chin_lift	0=no 1=yes	categorical/no minal	Table 3	P% x/n	intra
41.	CRF	Mask ventilation	Mask_vent	0=no 1=yes	categorical/no minal	Table 3	P% x/n	intra
42.	CRF	general anesthesia	anesth	0=no 1=yes	categorical/no minal	Table 3	P% x/n	intra
43.	CRF	Tachycardia >100	Takykard	0=no 1=yes	categorical/no minal	Table 3	P% x/n	intra
44.	CRF	Bradycardia <40	Bradykard	0=no 1=yes	categorical/no minal	Table 3	P% x/n	intra
45.	CRF	Bradycardia treatment	brady treat	0=atropine 1=efedrin	categorical/no minal	Table 3	P% x/n	intra
46.	CRF	Hypotension (SBP <90mmHg) or difference >30%	Low_SBP	0=no 1=yes	categorical/no minal	Table 3	P% x/n	intra
47.	CRF	Hypotension treatment	Hypo treat	0=vätska 1=sympatomimetic	categorical/no minal	Table 3	P% x/n	intra
48.	CRF	nausea	nausea	0=no 1=yes	categorical/no minal	Table 3	P% x/n	intra
49.	CRF	Patient back to post op time	Back_DU VA	Hh:mm	continuous	Table 3	n, Median, min max, IQR	post
50.	CRF	Patient leaving post op time	Disch_DU VA	Hh:mm	continuous	Table 3	n, Median, min max, IQR	post

51.	CRF	Postop time	Postop time	Leave postop (hh:min) – arrive postop (hh:min) efter procedure in minutes	continuous	Table 3	n, Median, min max, IQR	post U
52.	questionnaire	Overall satisfaction	Ov_satis	0-10	ordinal	Fig 1	n, Median, min max, IQR	post
53.	questionnaire	Satisfaction with staff	Staff_satis	0-10	ordinal	Fig 1	n, Median, min max, IQR	post
54.	questionnaire	Maximal pain(NRS) during procedure	NRS_max	0-10	ordinal	Fig 1	n, Median, min max, IQR	post
55.		1 no pain NRS 0-3 2 Moderate pain NRS 4-7 3 severe pain 8-10	NRS grupper	1-3	ordinal	Fig 1	n, Median, min max, IQR	post
56.	questionnaire	Maximal pain arm with infusion	Pain_arm	0-10	ordinal	Fig 1	n, Median, min max, IQR	post
57.	questionnaire	Satisfaction pain management	Pain_satis	0-10	ordinal	Fig 1	n, Median, min max, IQR	post
58.	questionnaire	Importance of sedation	Sed_import	0-10	ordinal	Fig 1	n, Median, min max, IQR	post
59.	questionnaire	Importance of control over sedation	Contr_import	0-10	ordinal	Fig 1	n, Median, min max, IQR	post
60.	QoR-15 post	15 items	QoR-15post	0-10	ordinal	Manus 2	n, Median, interkvartil	QoR-15 post
61.	QoR-15 tel	15 items	QoR-15 tel	0-10	ordinal	Manus 2	n, Median, interkvartil	QoR-15 tel

6 General Considerations

6.1 Data requisition

Descriptive patient data is supplied by the patient's journal Cosmic or the National Patient Overview (NPÖ).

Procedurerelated data, medical parameters, registration of sedationrelated events is supplied by the patient's anaesthesia journal. Trialspecific documentation is performed in electronic case report form (REDCap) and in the patient's anaesthesia journal.

Patient's self-reported intraprocedural pain assessment and satisfaction is registered on a patient inquiry. The inquiry is completed by the patient prior to discharge from the recovery unit.

6.2 Timing of Analyses

The final analysis will be performed after 340 patients are included in the trial. The trial ends with the last patient being the last subject of the trial.

The final analysis will be performed on data transferred to the file "database PACSPI 2", having been documented as meeting the cleaning and approval requirements of the Trial Steering Group (TSG).

6.3 Analysis Populations

6.3.1 Full Analysis Population

All participants who were randomized to either group satisfying the exclusion criteria.

6.3.2 Per Protocol Population

All participants who received a SVP and completed the patient questionnaire.

6.3.3 Intention to Treat Analysis

Analyses will be performed on all participants in the study and control arms respectively which they were randomized to following the intention-to-treat principle.

6.4 Subgroups

Subgroup analyses are planned on centre, gender, operator's experience, age, and cancer treatment strategy.

6.5 Missing Data

Missing data will be quantified and reported in the final manuscript by "common-point imputation".

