4.3 Study Objectives

The primary objective is to determine the efficacy of patient-controlled sedation (PCS) as adjunct to local anaesthesia (LA) on patients' self-reported pain perception during SVP-implantation. Patients in the treatment arm will undergo SVP insertion in LA combined with PCS and in the control arm SVP insertion will be conducted in LA.

The second objective is analyses of patient distress and satisfaction as well as secondary efficacy outcomes and determination of the relative safety of the treatment arm on defined safety outcomes and all adverse events and costs.

Primary endpoint: The primary endpoint is assessment of patient-reported pain perception. Endpoints are assessed by the use of the numeric rating scale (NRS):

- maximal intraprocedural pain level on NRS

Secondary endpoints:

- satisfaction with pain treatment during implantation
- maximal distress level
- importance of receiving sedatives during implantation
- overall satisfaction
- overall satisfaction with the staff
- maximal pain from arm with PCS infusion
- importance of being in control of sedation administration
- grading of implantation conditions by the implanting physician
- perioperative and procedural time consumption
- delivered doses of alfentanil and propofol
- rescue-therapy by nurse
- differences in cost
- vital parameters: oxygen saturation, heart rate, blood pressure
- sedation levels according to Observers Assessment of Alertness/Sedation scale (OAA/S)
- procedural data,
- Quality of Recovery-15 (QoR-15)

Safety endpoints:

- arterial puncture
- pneumothorax
- hypotension
- arrhythmia
- hypoxia
- airway intervention
- respiratory rate

5 Study Methods

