5.5 Withdrawal Criteria

Patients will be informed that they have the right to withdraw from the study at any time for any reason, without prejudice to their medical care. Full details of the reasons for withdrawal will be recorded on the Case Withdrawal Form (CWF) which must be completed if a patient wishes withdrawal from the study and send to the principal investigator. By withdrawal from the study previously collected data remains part of the study database. No subsequent data will be used after withdrawal.

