10.2 Causality and severity of AE and SAE

The principal investigator is responsible for judgement of causality and severity of reported AE/SAE and application of used medicinal products in this trial. Reporting is carried out on AE/SAE forms and the incident will be described and graded with date, causality, severity and result. Follow-up of patients with signs of AE/SAE is granted until the condition has subsided.

Causality: All AE are categorized according to the following definitions.

Probable causal relationship:

Evidence to suggest a causal relationship; the influence of other factors is unlikely.

Possible causal relationship:

Some evidence to suggest a causal relationship (e.g. occurrence within a reasonable time after administration of the trial medication), but other factors may have contributed to the event (e.g. another clinical condition or other concomitant treatment).

Unrelated causality:

No evidence of any causal relationship with the trial intervention.

Severity: All AE are categorized according to the following definitions.

Mild: AE results in awareness of sign or symptom, but easily tolerated

Moderate: AE results in discomfort sufficient to cause interference with normal activities

Severe: AE results in incapacitating, with inability to perform normal activities

11 Statistics and Data Analysis

Data will be summarised by treatment group. Number (n), median, interquartile range, minimum and maximum will summarise continuous efficacy variables, whereas number and percent will summarise categorical efficacy variables.

All analyses of the continuous efficacy variables will be performed as analysis of variance with the treatment group.

All summary tables will be structured with a column for each treatment and will be annotated with the total population size relevant to that table/treatment, including any missing observations.

Mann-Whitney U and Chi² will be used to test for comparison between groups, depending on whether data are discrete or continuous.

Primary objective: PCS with propofol and alfentanil as adjunct to LA reduces pain compared to LA only in SVP-implantation.

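### SAP 6.5 names an undefined 'common-point imputation' and leaves open whether and how a missing pain answer enters the primary comparison

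*SAP*

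**What the plan says.** SAP 6.5 consists of one sentence: "Missing data will be quantified and reported in the final manuscript by 'common-point imputation". The term occurs nowhere else in either document. No fill value, model, list of variables, missingness assumption or sensitivity analysis goes with it.

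The primary endpoint in SAP 4.3 is "maximal intraprocedural pain level on NRS". SAP 5.6 holds it as variable 54, "Maximal pain(NRS) during procedure", ordinal and coded 0-10. It comes from the patient form, which SAP 6.1 has completed before discharge from the recovery unit.

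On who is analysed, SAP 6.3.3 says: "Analyses will be performed on all participants in the study and control arms respectively which they were randomized to following the intention-to-treat principle". The per-protocol set in SAP 6.3.2 is: "All participants who received a SVP and completed the patient questionnaire". SAP 5.5 adds: "No subsequent data will be used after withdrawal".

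SAP section 11 says that summary tables "will be annotated with the total population size relevant to that table/treatment, including any missing observations", and that Mann-Whitney U and chi-squared "will be used to test for comparison between groups, depending on whether data are discrete or continuous". It does not say how either test treats a missing answer.

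SAP 6.6.3 states that the chief investigator and statistician who do the final analysis remain blinded through coded groups. Protocol 6.3 assumes data missing at random and under 10% missing. It belongs to the QoR-15 sub-study, names no imputation and does not govern the pain endpoint.

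**The concern.** Only the per-protocol set requires a completed questionnaire, so a randomised patient without a pain answer stays in the intention-to-treat set. SAP 6.5 is the only text in either document that could say what happens to that patient's score, and it does not. Two statisticians could follow it faithfully and report different primary results.

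If the term means inserting one common value, two things follow. Invented scores are counted as observed data. And if one arm has more missing answers, more copies of the same value land in that arm, which can create a difference between arms that the patients did not report. Unequal missingness is possible because staff and patients know the allocation (SAP 5.5.1). The documents give neither the fill nor the missingness by arm, so the size can only be shown over assumed ranges.

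**Working it through.** **1. The plan's own figure.** Inputs from SAP section 11: 25% of patients at NRS ≥4 under local anaesthesia, halved to 12.5%; 80% power; two-sided 5%; 1:1. Pooled two-proportion formula, mean rate 0.1875:

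n per arm = [1.96·√(2·0.1875·0.8125) + 0.8416·√(0.25·0.75 + 0.125·0.875)]² / 0.125² = 151.9, so 152 per arm and 304 in total.

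The SAP states 308, which is 1.3% more and gives 80.5% power at 154 per arm. For 10% drop-out, 308 × 1.1 = 339 and 308 / 0.9 = 343; the SAP's 340 is consistent with these. The sample size is not in dispute.

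**2. How a single fill creates a difference.** Assume no true effect, with 25% at NRS ≥4 in both arms, and q the share missing. A fill at the midpoint, 5, gives an expected share at ≥4 of (1−q)·0.25 + q.
- 2% vs 10% missing: 0.98·0.25 + 0.02 = 26.5% against 0.90·0.25 + 0.10 = 32.5%, a spurious gap of 6 points.
- 2% vs 5% missing: 26.5% against 0.95·0.25 + 0.05 = 28.75%, a gap of 2.25 points.
- Equal missingness: no gap.

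**3. False positives on the endpoint itself.** 0-10 score, tie-corrected Mann-Whitney, 170 per arm, two-sided 5%, 100,000 simulated trials per setting, no true effect. Assumed shapes: 25% of patients on scores 4-10, weighted 7:6:5:4:3:2:1; 75% on scores 0-3, weighted 4:3:2:1, equally, or 1:2:3:4. Missingness is unrelated to pain.

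| Handling of missing scores | 2% vs 10% missing | 2% vs 5% missing |
|---|---|---|
| Observed answers only | 5% | 5% |
| Pooled median | 5-6% | 5% |
| Midpoint (5) | about 14% | about 6% |
| Most common score | about 5-15%, highest if the mode is 0 | about 5-6.5% |

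With 10% missing in both arms, every fill stays at about 5%.

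**4. Power.** With 10% missing in both arms and the true effect of step 1, power against observed answers changes by −1 to −3 points for the pooled median and by about +1 for a fill of 4. Loss of power is therefore not universal.

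**5. The sample-size scale (NRS ≥4), as support only.** With 10% missing per arm, observed cases (153 per arm) have 80.3% power. Filling every missing score below 4 compares 22.5% with 11.25% and gives 79.4%. Filling every one at 4 or above compares 32.5% with 21.25% and gives 64.9%. The documents' rates put (25 + 12.5)/2 = 18.75% of patients at ≥4, so a pooled-median or most-common-score fill would fall below 4 and cost under one point.

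The fill can still decide significance. With 38 vs 24 patients at ≥4 among 153 observed per arm (chi-squared, no continuity correction), p = 0.046 on observed cases, 0.049 filled below 4, and 0.092 filled at 4 or above.

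**The case against.** The strongest reply is that little is at stake. The form is completed before discharge, so few pain answers may be missing; the 10% in SAP section 11 is a drop-out allowance, not a rate of missing answers. A pooled-median fill, one natural reading of the term, is nearly harmless. This stands as a limit on size. It does not settle the matter, because the SAP does not commit to the median, and a midpoint or most-common-score fill is an equally ordinary reading that does more when missingness is clearly unequal.

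Second, a reader might infer from the open-label design that the fill could be picked to suit the result. The documents do not support that: SAP 6.6.3 has the final analysis done blinded to group. Blinding does not, however, fix the fill or undo the distortion in step 2.

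Third, a reader might infer that 6.5 certainly sets the pain score of every patient without an answer. The sentence speaks only of quantifying and reporting, and does not name pain or any test. What stands is that the term is undefined and its reach unclear.

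Fourth, a reader might infer false-positive rates above 20%. A fill at 10 gives about 25% at 2% vs 10% missing, and a fill at 0 gives 15-23%. These need both an end-of-scale fill on this ground alone and an imbalance that no document states. A 0 fill is plausible only if 0 is the most common score, and then the figure is about 15%.

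Finally, observed cases are not automatically safe. On NRS ≥4 with no true effect and 2% vs 10% missing, false positives are 5% if missingness is unrelated to pain, 7.6% if half of the missing have NRS ≥4, and 17% if three quarters do. This is right, and it is why the fix includes sensitivity analyses. Defining the term alone would be the minimum cure, but it would still count invented scores as data.

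**Conclusion.** The point holds in a limited form: the only imputation wording in either document is undefined, it is unclear whether it reaches the primary test, and intention-to-treat patients can lack a pain answer. If it means one common fill, the primary result depends on a value not fixed in advance. The harm ranges from negligible (pooled median, or equal missingness for the false-positive rate) to a false-positive rate of about 14-15% (midpoint, or most common score when that is 0) at 2% vs 10% missing, and falls to at most about 6.5% at 2% vs 5%.

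These figures rest on the single-value reading, on assumed missingness by arm, on three assumed score shapes and on Mann-Whitney as the test. None of this shows that the trial's result will be wrong, and the real effect may be small. This is a cheap improvement.

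**What to change.** Before outcome data are examined, delete 'common-point imputation' from SAP 6.5 and write:

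> No single value is filled in for any outcome. Maximal pain NRS and the other questionnaire items (variables 52-59) are analysed on observed answers from all randomised patients in the arm to which they were randomised, with missing answers reported by arm. Sensitivity analyses for maximal pain NRS: (1) multiple imputation of the 0-10 score by arm, using age, gender, ASA class, centre, treatment strategy, operation time and rescue sedation; (2) best-case/worst-case bounds for NRS ≥4. QoR-15 is analysed in the separate sub-study plan.

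The bounds count missing as ≥4 in one arm and <4 in the other, then the reverse. Around an observed difference of 12.5 points with a share q missing per arm they are (1−q)·12.5 ± 100q points: 9.1 to 15.1 at 3% missing, 6.9 to 16.9 at 5%, and 1.25 to 21.25 at 10%. They are informative when few answers are missing.

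The cost is SAP wording and a little more analysis work, with no new data or patients. The downside is that the observed-case result leaves out patients with no pain answer, so it comes close to the per-protocol set, and it is unbiased only if missingness is unrelated to pain given arm. The two sensitivity analyses examine that and bring all randomised patients back in.

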6.6 Interim Analyses and Data Monitoring

6.6.1 Interim Analyses and Data Quality

Interim analyses are not expected to lead to early closure of neither randomization on safety nor efficacy grounds. Both techniques are established and clinically approved methods and complications are very uncommon. After 100 respectively 200 patients analyses of adverse events (AE) will be performed in which we expect a frequency lower than 15% based on previous studies [10]. In the event of a higher frequency the sponsor will discuss further action with the monitor (futility analysis might be considered).

Data validation will be performed after 5 and 10 patients were included in the trial to control REDCap´s functionality.

All staff involved in the trial will be informed on aim, progression, design and everything that lies in the staff´s responsibility according to profession.

Primary data sources are defined as patient journal, anaesthesia journal, e-CRF and patient inquiry and access will be granted to the monitor and controlling institutions on request. The required informed consent is included in the patient information/consent form.

6.6.2 Stopping Rules

No stopping rules apply.

6.6.3 Bias

Due to the nature and effects of sedative medication study participation is unblinded for both staff and participants. All patients scheduled for SVP will be screened for inclusion into the trial. The final analysis is performed by the chief investigator and statistician who remain blinded due to assessor blinding and coding in randomized groups.

6.7 Multi-centre Studies

This trial will be carried out in the following anaesthesia departments:

OP/IVA-kliniken, County Hospital Ryhov, Sweden

AnOpIVA-kliniken, University Hospital Linköping, Sweden

Co-investigators at participating sites will have access to the REDCap. Centres are provided with the PCS pump. There will be no restrictions in the choice of LA-solution being left up to local practice at participating sites

6.8 Multiple Testing

Not applicable

7 Summary of Study Data

7.1 Data collection

All patients will be registered at OP/IVA department, County Hospital Ryhov, Jönköping, Sweden. For all data being collected see list of variables (section 5.5).

The following data will be recorded:

- a) Demographic data: including patient's age, gender, date of birth, length, weight, ASA-classification
- b) Tumour presence: chemotherapy strategy
- c) Device details: manufacturer, type, previous long-time access
- d) Procedure details: implanting conditions, operator status, type and amount of local anaesthetic, access vein, number of needle passes, line tip position, use of ultrasound,
- e) Vital parameters: heart rate, blood pressure, oxygen saturation at baseline
- f) Sedation assessment: depth of sedation at four time points, administered amount of sedation/analgesic agents, need for rescue sedation and reason
- g) Complication data: procedural complications, vital parameters complications due to sedation, unexpected airway management
- h) Periprocedural time consumption
- i) Health economic aspects
- j) Patient's pain perception and satisfaction: questionnaire before discharge
- k) QoR-15: at 3 timepoints, pre- and postoperatively and one day after discharge

